7.2 SERIOUS ADVERSE EVENTS

Information about all serious adverse events (SAEs) will be collected and recorded on the Serious Adverse Event Report Form. To ensure patients' safety each SAE must also be reported to [REDACTED] within 24 hours of learning of its occurrence.

An SAE is an undesirable sign, symptom or medical condition which:

1. Is fatal or life-threatening.
2. Requires or prolongs hospitalization.
3. Results in persistent or significant disability/incapacity.
4. Constitutes a congenital anomaly or a birth defect.
5. Is medically significant, in that it may jeopardize the patient and may require medical or surgical intervention to prevent one of the outcomes listed above.

Events not to be reported as SAEs are hospitalizations for the following:

- Routine treatment or monitoring of the studied indication, not associated with any deterioration in condition, like training for the study drug administration, hospitalization for the period of pharmacokinetic sampling.
- Treatment, which was elective or pre-planned for a pre-existing condition that is unrelated to the indication under study and did not worsen.

OPKO Biologics	Protocol for Clinical Study CP-4-004	Page 89 of 133
Effective Date: Date of final electronic approval		

- Admission to a hospital or other institution for general care not associated with any deterioration in condition.
- Treatment on an emergency, outpatient basis for an event not fulfilling any of the aforementioned definitions of “serious” and not resulting in hospital admission.

The period for collecting and reporting SAEs for this study starts after the patient has provided assent (where applicable) and the parent(s)/guardian(s) has provided written informed consent, and continues until the formal end of study-notification.

7.2.1 Notification of Serious Adverse Events

7.2.1.1 Reporting responsibility

Each serious adverse event (SAE) must be reported by the investigator to the [REDACTED] Safety group within **24 hours of learning of its occurrence**, even if it is not felt to be treatment-related. Follow-up information about a previously reported SAE must also be reported within 24 hours of the investigator receiving it. If the SAE is unexpected and is thought to be possibly related to the study drug, a Clinical Safety Associate shall urgently request further information from the investigator. This is essential for collecting information to report to the competent regulatory authority (RA). All safety information obtained will be provided to the DSMB for review and assessment. The DSMB in collaboration with the sponsor will assess any suspected unexpected serious adverse reaction (SUSAR) occurring during the study to determine whether additional risks are imposed on patients and make a decision as to suspending further enrollment until a final decision has been made. The Sponsor may need to issue an investigator notification, to inform all investigators involved in any study with the same drug (or therapy) that this SUSAR has occurred.

7.2.1.2 Reporting procedures

The investigator must complete the Serious Adverse Event Report Form in English, assess the relationship to study treatment, and submit it electronically via eCRF within 24 hours to [REDACTED] CRO.

Follow-up information is to be submitted on a new SAE Form. The new form should clearly state that it is a follow-up to the previously reported SAE and give the date of the original report. The follow-up SAE report should describe whether the event has resolved or continues, if and how it was treated, and whether the patient continued or discontinued study participation.

OPKO Biologics	Protocol for Clinical Study CP-4-004	Page 90 of 133
Effective Date: Date of final electronic approval		

7.2.1.4 Information to include on SAE form

The following information should be provided in the SAE form to accurately and completely record the event:

1. Investigator name and site address.
2. Patient study identification number.
3. Patient's initials.
4. Patient demographics (gender, date of birth or age, weight, height).
5. Clinical Event:
 - Description
 - Date and time of onset, stop date, or duration
 - Severity
 - Treatment (including hospitalization)
 - Relationship to study drug (causality)
 - Action taken regarding study drug
 - Information on recovery and any sequelae
 - If the SAE resulted in death

OPKO Biologics	Protocol for Clinical Study CP-4-004	Page 91 of 133
Effective Date: Date of final electronic approval		

- Cause of death (whether or not the death was related to study drug)
- Autopsy findings (if available)
- Medical History case report form (copy)
- Concomitant Medication case report form (copy)
- Any relevant reports (laboratory, discharge, etc.)

Accompanying documentation, such as copies of hospital case reports, autopsy reports, and other documents when applicable, should be summarized on the SAE form and a copy of the source document may be sent if required. The patient's personal details will be removed and replaced with study identifiers i.e. study number and initials, if applicable.

Reporting of SAEs and other relevant safety information to the Health Authorities, Ethics Committees, Principal and Coordinating Investigators and Trial Investigators required by the above-mentioned functionaries and institutions will be fulfilled according to the current local laws and guidance. The detailed reporting duties and division of responsibilities between the sponsor and [REDACTED] CRO will be detailed in a separate document (Medical Management Manual). Once an event has been assessed as a SUSAR, then information must meet the expedited reporting requirements to the local regulatory authorities. The investigator is obliged to familiarize herself/himself with the reporting requirements for investigators in her/his country. The monitor can help with this.

7.3 ANTICIPATED ADVERSE EVENTS

Frequent AE in children are related to viral infections and bacterial infections:

Upper respiratory infection, lower respiratory infection, tonsillitis, ear infection, gastroenteritis, skin infection, allergic disease, asthma, arthritis, trauma secondary to physical activity, fracture, scoliosis.

Frequent symptoms in children are: weakness, fever, headache, hoarseness, cough, headache, dizziness, earache, abdominal pain, diarrhea, constipation, leg pains, musculo-skeletal pain, arthralgia, pruritus, skin rash, injection site pain, injection site swelling.

Frequent operations in children are: Tonsillectomy, adenoidectomy, acute appendicitis

7.4 PREGNANCY REPORTING AND FOLLOW-UP

For female child, it is possible that she may enter puberty during the course of the study and could theoretically become pregnant. As she cannot continue in the study if she were to become pregnant, the study physician is obligated to discuss this issue ahead of time with the patient and her parents. Study participants are requested to refrain from sexual activity during the study i.e. observe complete sexual abstinence as the only acceptable contraceptive measure in this study.

Furthermore, pubertal female child should undergo urine pregnancy test at each upcoming visit including EOS visit.

OPKO Biologics	Protocol for Clinical Study CP-4-004	Page 92 of 133
Effective Date: Date of final electronic approval		

If a patient were to become pregnant or thinks she may have become pregnant during the study, study physician should be informed immediately, such information will be recorded in study documentation and the patient will be asked to stop taking the study medication as it may cause unforeseen risks to the unborn baby. Serum pregnancy test will be scheduled immediately in such cases, and in the case of the negative result the test should be repeated in 2 weeks to confirm or exclude the pregnancy. In case of negative test results the patient will be offered to remain in the study and complete the remaining study procedures as scheduled. The pregnancy will be reported to the Medical Monitor, pharmacovigilance and sponsor and follow up period on mother and child will be defined based on individual basis and per discussion with DSMB.

For male participant, the study physician is obligated to discuss this issue of possible conception ahead of time with the male patients and his parents. Study participants are requested to refrain from sexual activity during the study i.e. observe complete sexual abstinence as the only acceptable contraceptive measure in this study.

If partner of the male patient becomes pregnant, study physician should be informed immediately. The patient mustn't stop taking the study medication. The pregnancy will be reported to the Medical Monitor, pharmacovigilance and sponsor and follow up period on mother and child will be defined based on individual basis and per discussion with DSMB.

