LT-OLE starts from the 2nd year of OLE (i.e. the 3rd year of treatment in the study) until transition to PEN (LT-OLE-PEN period). Patients in Cohorts 1 and 2 entering the LT-OLE will be switched to the highest MOD-4023 dose 0.66 mg/kg/week after signing a separate informed consent (unless a different medical decision was made). In case patients from Cohorts 1 and 2 have already entered the 2nd year of OLE, the switch to 0.66 mg/kg/week will be done at their next study visit after signing a separate informed consent. Patients in Cohort 3 will continue receiving 0.66 mg/kg/week.

If the IGF-I value will be above +2.0 SDS, patients will be requested to return to the clinic within 4-6 weeks for another evaluation. If IGF-I level value will continue to be above +2.0 SDS, the dose will be reduced by 15% to 0.56 mg/kg/week. Patients with reduced dose will be required to return to the clinic within 4-6 weeks for another IGF-I evaluation. If IGF-I level value is still above 2.0 SDS, the dose will be reduced again by 15% to 0.48 mg/kg/week. Patients, who had their dose reduced twice and who still have IGF-I level above 2.0 SDS within 4-6 weeks of second dose reduction, will be required to have individual medical consultation with the Medical Monitor (with the assistance of the DSMB if necessary).

Patients who are off treatment for [REDACTED] days between the last MOD-4023 in the OLE period and the first LT-OLE dose (3rd year) will be allowed to continue into the LT-OLE period after the following samples for testing will be collected

- Parameters of glucose metabolism: fasting glucose, insulin, and HbA1c

OPKO Biologics	Protocol for Clinical Study CP-4-004	Page 12 of 133
Effective Date: Date of final electronic approval		

- Antigenicity –anti MOD-4023 antibodies
- Routine safety laboratory (biochemistry, hematology, and urinalysis)
- PD: IGF-I and IGFBP-3 baseline serum levels
- MOD-4023 baseline serum levels

During LT-OLE, all patients will be assessed once every 3 months, as specified in the Schedule of Assessment, including: auxology measurements (actual height measured on a calibrated stadiometer and body weight measurement); adjustment of dose for weight; AEs; local tolerability; concomitant medication; and dispensing of drug.

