In addition, IGF-I, IGFBP-3 and MOD-4023 serum levels will be assessed every 6 months on day 3 or 4 post dosing. Once a year, patients will be required to attend another visit on dosing day (in addition to the semi-annual visit on day 3 or 4 post dosing) where the following additional assessments will be conducted (on top of the three and six months assessments): antigenicity (anti MOD-4023 antibodies), MOD-4023 serum levels, Physical examination, Vital signs, Parameters of glucose metabolism (fasting glucose, fasting insulin and HbA1c), Routine safety laboratory (biochemistry, hematology and urinalysis), other hormonal levels (TSH, free T4, free T3 and cortisol), lipid metabolism parameters, pubertal status, ECG, bone age, fundoscopy (if required), and for males that are 13 years old and above: LH, FSH and testosterone. For females that are 12 years old and above: LH, FSH and estradiol.

All patients switching to 0.66 mg/kg/week (e.g. patients from cohort 1 & 2 treatment arms) will be required to attend a site visit after 3 months (on day 3 or 4 post-dosing) for the process following evaluations: physical examination and vital signs, patient's height and weight, concomitant medications, glucose metabolism parameters (fasting glucose, insulin and HbA1c), antigenicity (anti MOD-4023 antibodies), routine safety laboratory (biochemistry, hematology and urinalysis) and IGF-I and IGFBP-3 serum levels.

In case the switch to the 0.66 mg/kg/week dose is on month 9 visit, the 3 months follow up visit will take place on dosing day. Additional visit will take place 3-4 days post dosing in which only IGF-I, IGFBP-3 and MOD-4023 serum levels will be measured.

Patients from cohort 3 should continue with their routine visit schedule.

Patients will sign a separate informed consent to be eligible to enter OLE and LT-OLE. Patients who have already entered OLE will be re-consented for LT-OLE. Patients from Cohorts 1 and 2 will be instructed by the investigator about the transition to the higher dose of MOD-4023 (0.66 mg/kg/week) and will also be re-consented.

Annual extension notification will be submitted to local EC/IRB.

Effective Date: Date of final electronic approval

Treatment Period V (LT-OLE-PEN) – until marketing approval**First year of LT-OLE-PEN period**

Upon regulatory clearance of protocol amendment 9 and sponsor written approval, patients will be requested to come to the clinic for PEN Visit 1(PEN V1).

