All visit windows will be on scheduled days or -1 day (except visit 9 main study) for MOD-4023 dose cohorts unless it's specified otherwise. The study flow chart provides the summary of assessments scheduled for each visit during the Main Study (Appendix 1), 12 months OLE study (Appendix 2), Long Term OLE (LT-OLE) period (Appendix 3) and Long Term OLE PEN (LT-OLE-PEN) period (Appendix 4 and Appendix 5). At each visit after start of treatment, patients will be given enough Investigational or Comparator Product for treatment until the next visit, as well as patient diary cards to record injection pain or other adverse events and other comments.

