5.3 LONG-TERM OPEN LABEL EXTENSION (LT-OLE) PERIOD IV

LT-OLE starts from the 2nd year of OLE (i.e. the 3rd year of treatment in the study) and until transition to PEN (LT-OLE-PEN period).

Patients in Cohorts 1 and 2 entering the LT-OLE will be switched to the highest MOD-4023 dose 0.66 mg/kg/week after signing a separate informed consent (unless a different medical decision was made). In case patients from Cohorts 1 and 2 who have already entered the 2nd year of OLE, the switch to 0.66 mg/kg/week will be done at their next study visit after signing a separate informed consent. Patients in Cohort 3 will continue receiving 0.66 mg/kg/week. All patients switching to 0.66 mg/kg/week will be required to attend a site visit after 3 months (on day 3 or 4 post-dosing) for the following evaluations: physical examination and vital signs, patient's height and weight, concomitant medications, glucose metabolism parameters (fasting glucose, insulin and HbA1c), antigenicity (anti MOD-4023 antibodies), routine safety laboratory (biochemistry, hematology and urinalysis), IGF-I and IGFBP-3 serum levels. In case the switch to the 0.66 mg/kg/week dose is on month 9 visit, the 3 months follow up visit will take place on dosing day. Additional visit will take place 3-4 post dosing in which only IGF-I, IGFBP-3 and MOD-4023 serum levels will be measured.

In general, if the IGF-I value will be above +2.0 SDS, please refer to section [5.8.3](#).

Patients who are off treatment for over [REDACTED] between the last MOD-4023 in the OLE period and the first LT-OLE dose (3rd year) will be allowed to continue into the LT-OLE period after the following tests and assessments will be conducted:

- Parameters of glucose metabolism: fasting glucose, insulin, and HbA1c
- Antigenicity: anti MOD-4023 antibodies
- Routine safety laboratory (biochemistry, hematology, and urinalysis)
- PD: IGF-I and IGFBP-3 baseline serum levels
- MOD-4023 baseline serum levels

The following assessments will be conducted once every 3 months (13 ±2 weeks) during LT-OLE (on day 4 (-1) post dose):

- Auxology measurements: Actual height measured on a calibrated stadiometer and body weight measurement;
- Adjustment of dose for weight;
- AEs;
- Local tolerability;
- Concomitant medication;
- Dispensing of drug and return of used drug
- Patient diary dispensing and return of completed diaries

OPKO Biologics	Protocol for Clinical Study CP-4-004	Page 60 of 133
Effective Date: Date of final electronic approval		

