The following assessments will be conducted every 6 months (± 2 weeks) on day 4 (-1) post dose on top of the 3 month assessments:

- IGF-I, IGFBP-3 and MOD-4023 serum levels.
- Once a year, patients will be required to attend another visit **on dosing day** (in addition to the semi-annual visit on day 3 or 4 post dosing) where the following additional assessments will be conducted (on top of the three and six months assessments):Anti-MOD-4023 antibodies;
- MOD- 4023 serum levels
- Physical examination;
- Vital signs;
- Parameters of glucose metabolism (fasting glucose, fasting insulin and HbA1c);
- Other hormonal levels (TSH, free T4, free T3, cortisol);
- Parameters of lipid metabolism;
- Routine safety laboratory (biochemistry, hematology and urinalysis);
- Pubertal status;
- ECG;
- Bone age;
- For males above the age of 13 - LH, FSH and testosterone. For females above the age of 12 - LH, FSH and estradiol;
- Fundoscopy (if indicated).

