5.5 UNSCHEDULED AND EARLY TERMINATION VISITS

5.5.1 Unscheduled Visits

Unscheduled visits are those visits that will occur between regularly scheduled visits and will be performed in order to assess a previously noted adverse event, abnormal/alarming laboratory values, and or clinical findings. In such cases, the patient's parent or legal guardian will be contacted via telephone to arrange an unscheduled visit to assess the noticed abnormalities. Only focused assessments are foreseen for these visits and there will be no need to collect very extensive additional laboratory or other safety and efficacy data. If blood collection is required, this should in principle not exceed the volume foreseen for the assessment of questionable/targeted parameter(s) and/or should not be over 50% of volume foreseen for the routine safety panel at regularly scheduled visits. If urgent or more convenient for the patient, a local laboratory can be used.

According to point 4.5.4 of GCP-ICH, the investigator may implement a deviation form, or a change in the protocol, to eliminate an immediate hazard to a trial patient without prior IRB/IEC approval/favorable opinion. In this case the IRB/IEC will be notified retrospectively.

5.5.2 Early Termination and End of Study Visits – Main Study, OLE, LT-OLE and LT-OLE-PEN Periods

Early termination visits are appointed for the early termination/withdrawal of a patient from this clinical study. These visits may be performed on the same day as originally scheduled visits, or appointed separately. Data collection from these visits should primarily be guided according to GCP principles, protecting patient's safety and wellbeing. The schedule of assessments for early termination and end of study visits (both for patients in the Main Study and for those in other study periods) should follow those **requested for the last Study visit**

OPKO Biologics	Protocol for Clinical Study CP-4-004	Page 67 of 133
Effective Date: Date of final electronic approval		

(i.e. month 12) of each period. The structure of early termination visit should be as much as possible similar to the last study visit.

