5.7.1.4 Hormonal status with special attention on thyroid and adrenal status

Cortisol: Blood cortisol should be monitored throughout the study since GH treatment may unmask previously undiagnosed or sub-clinical central hypoadrenalinism.

Supra-physiological glucocorticoid treatment may attenuate the growth promoting effect of somatropin (as for asthma). Therefore, children requiring a glucocorticoid dose of greater than 400 µg/d of inhaled budesonide or equivalents (approximately equivalent doses: Fluticasone: 264 µg/d; Beclomethasone: 504 µg/d; Flunisolide 1,000 µg/d; Triamcinolone: 1,000 µg/d) for longer than 1 month during a calendar year will not be included in the study or may be discontinued if additional dosing is required.

Thyroid hormones: Blood TSH and T4 should be monitored throughout the study since GH treatment may unmask previously undiagnosed or sub-clinical central hypothyroidism. Undiagnosed/untreated hypothyroidism attenuates growth and metabolism. Upon diagnosis of hypothyroidism, thyroid hormone replacement therapy should be initiated following approval by Coordinating Investigator. Thyroid dose should be adjusted throughout the study so that T4 levels will be close to the median range.

Gonadotrophic hormones - (applicable only for the LT-OLE and LT-OLE-PEN periods) - FSH, LH and Estradiol for females that are 12 years old and above and LH, FSH and testosterone for males that are 13 years old and above.

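### Protocol 7.4 requires a urine pregnancy test for pubertal girls at each visit including end of study, but the Period IV (LT-OLE) visit schedule lists none

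*Protocol*

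**What the plan says.** **The rule.** Protocol 7.4 notes that a girl may enter puberty while in the study and then says that a "pubertal female child should undergo urine pregnancy test at each upcoming visit including EOS visit". It names no study period.

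**The Period IV schedule.** The synopsis says "During LT-OLE, all patients will be assessed once every 3 months, as specified in the Schedule of Assessment" and then names the assessments. Its yearly list includes pubertal status and "For females that are 12 years old and above: LH, FSH and estradiol". Section 5.3 gives a quarterly list, introduced by "The following assessments will be conducted once every 3 months", then a six-monthly item and a yearly list that again includes pubertal status and "For females above the age of 12 - LH, FSH and estradiol". None of these contains a pregnancy test.

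**How sites are directed.** The introduction to Section 5 says "The study flow chart provides the summary of assessments scheduled for each visit" and names Appendix 3 as the chart for LT-OLE. Section 5.5.2 says that "The schedule of assessments for early termination and end of study visits" is to follow what is requested at month 12 of the period concerned.

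**The contrast with Period V.** Section 5.7.1.4 describes the gonadotrophic hormone measurements as "applicable only for the LT-OLE and LT-OLE-PEN periods", so puberty monitoring by hormones covers Periods IV and V alike. Only the Period V text (5.4.1, 5.4.2, Appendices 4 and 5) schedules a urine pregnancy test, with a positive result referred to 7.4.

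**The SAP.** The Period IV chart in SAP 4.3 has no pregnancy test row, while the Period V charts do. Listing 16.2.8.10 in SAP 11.2 lists pregnancy test results.

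**The concern.** Two operative parts of the protocol give different instructions for the same visits. Section 7.4 asks for a test at each visit, whereas the Period IV schedule asks for none. Coordinators normally run a visit from the schedule, and the protocol directs them there, so the schedule is the instruction more likely to be followed.

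What is at stake is safety conduct. Section 7.4 says that a pregnant girl cannot continue and that the drug may carry unforeseen risk to the unborn child. If the test is not done, detection in Period IV depends on the girl or her family reporting a suspected pregnancy, and a pregnancy during weekly dosing could be found later than 7.4 intends.

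**Working it through.** No figure in the plan needs reproducing. The check sets the rule beside every list of assessments and counts the pregnancy test entries.

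| Place | What was counted | Entries with the test |
|---|---|---|
| Synopsis, Period IV | 3-monthly, 6-monthly and yearly text | 0 |
| 5.3 | 7 quarterly + 1 six-monthly + 13 yearly = 21 bullets | 0 of 21 |
| 5.3, restart list and visit 3 months after the dose switch | both lists | 0 |
| Appendix 3 | 13 rows on its first page + 8 on its second = 21 rows | 0 of 21 |
| SAP 4.3, Period IV chart | all rows, including the 12-month/end of study column | 0 |
| Appendix 4 (Period V, first year) | PEN V1, PEN V2, months 3, 6, 9, 12 = 6 columns | 6 of 6 |
| Appendix 5 (Period V, later years) | months 3, 6, 9, 12 = 4 columns | 4 of 4 |

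These rows record one omission seen in several places. They show that it is consistent, not how many girls it affects.

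**Could another section supply the test?** Section 5.5.2 does not, because it sends early termination and end of study visits back to the period's month 12 list, which has no test. Appendix 3 has its own early termination and Month 12/end of study columns, and neither contains one. The end of study test that 7.4 names is therefore unscheduled in Period IV.

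**Is it lost table text?** That is unlikely. The synopsis prose, the prose lists in 5.3, the Appendix 3 table and the SAP chart all omit the test, while their Period V counterparts all include it.

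**Are pubertal girls expected in Period IV?** Yes. Girls enrol up to age 10 (4.1), and Period IV begins with the third year of treatment (5.3), that is, after 2 years. The oldest are then about 10 + 2 = 12 at entry, which is the age from which Period IV measures LH, FSH and estradiol.

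**Who is exposed to the gap?** A girl who switches to the pen is tested before her first pen dose at PEN V1 (5.4.1.1). The gap therefore concerns visits within Period IV, and girls who leave the study from Period IV and never reach PEN V1.

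**The case against.** The strongest objection is that 7.4 was meant for Period V. The abstinence criterion in 4.1 and the discontinuation rule for a positive test in 4.6 are both headed as specific to that period. Every referral of a positive test to 7.4 sits in Period V text, and the reference to upcoming visits could be read as looking forward from the pen amendment. This reading is plausible, but 7.4 does not state it. The protocol labels Period V provisions where it means them, and 7.4 carries no label and speaks of puberty arising during the study. If Period V alone was intended, 7.4 still needs correcting.

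A second objection is that 7.4 is itself binding text and that the flow chart is only a summary, as shown by Appendix 3 also lacking the fundoscopy that 5.3 lists. This stands in part. A reader might infer that girls in Period IV have no pregnancy safeguard, and the documents do not support that: the test requirement, counselling, abstinence request, serum confirmation, stopping of drug and reporting in 7.4 all apply there. What is missing is the scheduled test.

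A third objection is that Period III has the same gap if 7.4 covers all periods, since Appendix 2 has no test although pubertal status is recorded at its month 12. That is correct. The point is confined to Period IV because hormone monitoring of puberty starts there.

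**Conclusion.** The conflict is real and should be corrected. It is an inconsistency between a safety rule and a visit schedule, and it touches no endpoint, sample size, efficacy estimate or statistical analysis.

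Its size in girls or visits cannot be determined. The documents give neither the number of pubertal girls in Period IV nor the time left in that period before the pen switch under version 10. The number is probably small. The conclusion assumes that 7.4 applies as written, without a period limit, and that sites work mainly from the schedule.

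Two further inferences would go too far:
- **That Period V tests at literally every visit.** All columns of Appendices 4 and 5 carry the test, but month 12 of the first pen year is split into two visits. By 5.4.1.5 the day 4 visit assesses only IGF-I and IGFBP-3; the test belongs to the dosing-day visit.
- **That the SAP can stay as it is because Listing 16.2.8.10 exists.** The listing covers the output, but the Period IV chart in SAP 4.3 would be out of step with an amended protocol.

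**What to change.** Add a urine pregnancy test to the Period IV text of the synopsis, to 5.3 and to Appendix 3, as follows:
- at each 3-monthly visit;
- once at the Month 12 visit, which is split between dosing day and day 4, so that a girl is not tested twice within days;
- at early termination and end of study;
- with a positive result referred to 7.4, as in Appendices 4 and 5.

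Use one term for who is tested. Section 7.4 speaks of pubertal girls, while Appendices 4 and 5 speak of females of child bearing potential.

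Add the same row to the Period IV chart in SAP 4.3. Listing 16.2.8.10 already covers the results, so no table or analysis changes. If the sponsor meant the rule for Period V only, 7.4 should say so and explain why Period IV is exempt.

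The cost is one urine test per eligible girl at visits she already attends, one row in Appendix 3, one line each in 5.3 and the synopsis, and one row in the SAP chart. It adds no visit, and no procedure beyond what 7.4 already requires.
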